6. STUDY TREATMENTS

Study treatment is defined as any investigational treatment(s), marketed product(s), or medical device(s) intended to be administered to a study participant according to the study protocol.

All IMPs required for completion of this study will be provided by the Sponsor. All non-investigational medicinal products (NIMPs) required for completion of this study will be either provided or reimbursed by the Sponsor.

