7.1 DISCONTINUATION/INTERRUPTION OF STUDY TREATMENT

Reasons for discontinuation or interruption of study treatment (or withdrawal from the study) may include, but are not limited to, the following:

- Participant withdrawal of consent at any time
- Participant non-compliance with study requirements
- Any medical condition or AE/laboratory abnormalities that the Investigator or Sponsor determines may jeopardize the participant's safety if he or she continues in the study
- Investigator or Sponsor determination that treatment discontinuation is in the best interest of the participant
- Pregnancy

- CHB disease progression (e.g., development of liver cirrhosis or liver decompensation)
- Confirmed virological breakthrough

For management of virological breakthrough see Section 8.3.8.1; for ALT elevations see Section 8.3.8.3, and for NME-related adverse events refer to the respective appendix of each treatment arm for details.

Before permanently discontinuing study treatment (regardless of whether initiated by the participant, the Investigator, or the Sponsor), an interruption should be considered. Unless otherwise stated in the respective appendix of each treatment arm, participants who have temporarily interrupted study treatment should be considered to restart as soon as medically justified in the opinion of the Investigator. The Medical Monitor is available to the Investigator to answer any medical questions.

Table 2 below serves as a reference guide for the reasons of study treatment discontinuation/interruption which may occur in the study.

Table 2 All Combination Arms: General Criteria for Dose Interruptions/Discontinuations for All New Molecular Entities

The Trapholis / Discontinuations to		
Laboratory/Clinical Parameters	Recommendation	Reference
Liver transaminases and liver function test		
ALT elevation >10 × ULN (with preserved hepatic function)	Interrupt NMEs, continue NUC. Resume NMEs when ALT <3 × ULN (case-by-case basis)	Section 8.3.8.3
ALT >3 \times ULN accompanied by declining liver function (total bilirubin >2 \times ULN, or INR >1.5 or albumin <3.0 g/dL), or other signs of hepatic impairment	Discontinue NMEs, continue NUC. Investigate the etiology and including potential DILI	
Virological breakthrough		
Confirmed virological breakthrough	Discontinue NMEs and continue treatment according to local standards	Section 8.3.8.1
Others (excluding consent withdrawal and non-complian	ce)	

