Any clinically-significant AEs or laboratory abnormalities that in the opinion of Investigator may be related to NME(s)	Interrupt NME(s) until AEs/laboratory abnormalities are resolved. Re-introduce NME(s) (on a case-by case basis, which may be at a modified dose if deemed necessary)	
Any medical condition or AE/laboratory abnormalities that the lnvestigator or Sponsor determines may jeopardize the participant's safety if he or she continues in the study		Section 7.1
Sponsor or Investigator determination that treatment discontinuation is the best interest for the participant	Discontinue NMEs, continue NUC	
Pregnancy		
CHB disease progression		

Every effort should be made to obtain information on participants who withdraw from the treatment but have not withdrawn from the study. Participants who permanently discontinue study treatment will be asked to return to the clinic for an unscheduled/early

termination visit and will undergo follow-up assessments. The primary reason for premature study treatment discontinuation should be documented on the appropriate eCRF.

Participants, who permanently discontinue study treatment as part of an early termination of a treatment arm due to Sponsor's decision, will undergo safety follow-up assessments as described in Appendix 6. For participants who are in treatment arms NOT terminated by the sponsor, will proceed as planned and undergo follow up as per the SOA of the respective treatment arm.

Participants who discontinue study treatment due to non-safety reasons may be replaced.

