8.3.8.3 Management of Elevated Alanine Aminotransferase (ALT) Levels

The initial study population consists of CHB participants who are virally suppressed following > 12 months of NUC treatment. The majority of these participants (90%) have normal ALT levels, while approximately 10% have ALT levels within 1–2×ULN at baseline (Marcellin et al 2019).

For this study, close monitoring will be initiated if ALT elevations exceed $> 3 \times ULN$.

ALT elevations during treatment

- ALT elevation with preserved hepatic function (e.g., no significant changes in bilirubin, International Normalized Ratio [INR]/prothrombin time [PT], albumin, and/or alkaline phosphatase [ALP]):
 - ALT 3–10×ULN: *Repeat ALT, LFTs (including total bilirubin, direct bilirubin, AST, ALP, albumin), coagulation (INR, PT), and PD parameters (HBV DNA, HBsAg, quantitative HBeAg) every week until ALT< 3 × ULN.
 - ALT > 10 × ULN: Immediately interrupt NMEs and continue NUC treatment.
 *Repeat ALT, LFTs, coagulation, and PD parameters #twice weekly until ALT level < 10 × ULN, then weekly until ALT < 3 × ULN. Consider re-introducing NME therapy on a case-by-case basis based on subsequent lab results. The Medical Monitor is available to the Investigator to answer any medical questions.
- ALT elevation accompanied by declining liver synthetic and excretory functions (total bilirubin > 2×ULN, or albumin <3.0 g/dL, or INR >1.5) or other signs of hepatic impairment (severe fatigue, vomiting):
 - Immediately discontinue NMEs and continue NUC treatment.
 - *Repeat ALT, LFTs, Coagulation, and PD parameters #twice weekly until levels return towards baseline levels or normal range
 - o Investigate the participant for potential etiologies of the laboratory changes.
 - If alternative reasons/diagnoses cannot explain the laboratory changes, potential drug-induced liver injury (DILI) will be considered.

^{*}Frequency of monitoring may need to be adjusted based upon clinical scenario and severity of injury. * As the central laboratory results generation and reporting will take time, for

participant safety monitoring an additional local laboratory tests may be performed at the same time as the central laboratory test, and decision-making may be based on local laboratory results.

For marked and/or persistent ALT elevations, collect a spare serum sample (to allow retrospective evaluation of potential etiologies) and consider liver biopsy on a case-by-case basis (if deemed clinically relevant).

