While pregnancy itself is not considered to be an AE or SAE, and should not be recorded on the AE eCRF, any pregnancy complication will be reported as an AE or SAE. A spontaneous abortion is always considered to be an SAE and will be reported as such. Any post-study pregnancy related SAE considered reasonably related to the study treatment by the Investigator, will be reported to the Sponsor as described in Appendix 2. While the Investigator is not obligated to actively seek this information in former study participants, he/she may learn of an SAE through spontaneous reporting.

Any female participant who becomes pregnant while participating in the study will discontinue study treatment.

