When dose modification of PEG-IFN is required for adverse reactions (clinical and/or laboratory), an initial dose reduction to 135 μ g (adjustment to the corresponding graduation mark for the prefilled syringes) is recommended. Dose reduction to 90 μ g (adjustment to the corresponding graduation mark for the prefilled syringes) may be needed if the adverse reaction persists or recurs. Following improvement of the adverse reaction, re-escalation of the dose may be considered. Appendix 10-Table 2 provides guidelines for dose modifications and discontinuation of PEG-IFN for laboratory abnormalities as well as other NME dose interruption/discontinuation criteria.

Appendix 10-Table 2 Summary of Dose Interruption/Modification/Discontinuation Guidelines for siRNA+PEG-IFN+NUC Combination Arm

Laboratory/Clinical Parameters	Recommendation	Reference
siRNA-related AEs		
No laboratory and clinical parameters have been identified yet	No dose modification recommedations for siRNA	N/A
General criteria for dose interruptions/discontinuations for a	all NMEs	
Liver transaminases and liver function test	See Section 7.1	Section 8.3.8.3
Confirmed virological breakthrough	Discontinue NMEs and continue treatment according to local standards	Section 8.3.8.1
Others	See Section 7.1	
PEG-IFN-related AEs (only listed the most common AEs)*		
Neutropenia	ANC <750 cells/mm³: Reduce PEG-IFN to 135 µg. ANC <500 cells/mm³: Discontinue PEG-IFN until ANC >1000 cells/mm³· Resume PEG-IFN at 90 µg and monitor ANC.	
Thrombocytopenia	<50,000 cells/mm³: Reduce PEG-IFN to 90 μg. <25,000 cells/mm³: Discontinue PEG-IFN	Appendix 10 (Section
Persistent ALT elevation ≥5 - <10 × ULN	Reduce PEG-IFN to 135 μg. Monitor ALT weekly (further modifying dose if necessary) until ALT is stable or decreases	A10.10) *For details of management of PEG-
Persistent ALT values >10 × ULN	Temporarily interrupt , based on laboratory result consider re-introducing therapy	IFN-related AEs, pleas follow local prescribin information
New or worsening ophthalmologic disorders	Discontinue PEG-IFN	
Severe depression or suicidal ideation	Discontinue PEG-IFN and psychiatric intervention as appropriate	
Patients who develop or experience exacerbations of psoriasis	Discontinuation of PEG-IFN should be considered	

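### In the PEG-IFN arm no rule clearly says what happens to PEG-IFN when liver function declines, and the pregnancy instructions disagree on whether NUC continues

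*Protocol*

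**What the plan says.** **Liver rules for all combination arms.** For ALT above 10×ULN with preserved function, Section 8.3.8.3 says "Immediately interrupt NMEs and continue NUC treatment". Section 7.1 Table 2 gives the same action and allows NMEs to resume below 3×ULN, case by case. For an ALT rise with declining function (bilirubin above 2×ULN, INR above 1.5, albumin below 3.0 g/dL, or other signs), Section 8.3.8.3 says "Immediately discontinue NMEs and continue NUC treatment", and Table 2 agrees.

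**Liver rules for arm 5.** Appendix 10-Table 2 has one block of general criteria for all NMEs, which refers back to Sections 7.1 and 8.3.8.3, and a separate block for PEG-IFN-related events. The PEG-IFN block reduces the dose at persistent ALT from 5 to below 10×ULN and temporarily interrupts at "Persistent ALT values >10 × ULN". It has no row for bilirubin, INR or albumin. Section A10.11 introduces the table as covering PEG-IFN "as well as other NME dose interruption/discontinuation criteria".

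**Pregnancy.** Table 2, whose title limits it to the combination arms, lists pregnancy next to the action "Discontinue NMEs, continue NUC". Appendix 5, Section 4 says: "Any female participant who becomes pregnant while participating in the study will discontinue study treatment". Section 6 begins its definition: "Study treatment is defined as any investigational treatment(s), marketed product(s), or medical device(s) intended to be administered".

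**The concern.** A stop rule has to tell the site which drug to stop. Arm 5 has three kinds of drug: a novel siRNA, an approved interferon and background NUC. The general liver rules mention only two categories, NMEs and NUC. If PEG-IFN is not an NME, the strongest liver instruction in the protocol does not reach it. If it is an NME, its own ALT row is worded differently from the general rule.

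In pregnancy, one place appears to keep the antiviral going and another, on its wording, withdraws it.

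Two sites could therefore manage the same event differently and both cite the protocol, or a site could follow one page and deviate from another. PEG-IFN exposure and the liver-safety results of arm 5 would then depend partly on the page a site read. Appendix 6-Table 1 lists the arm as ongoing.

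**Working it through.** No design figure is involved, so the check sets the texts side by side.

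1. **Is PEG-IFN an NME?**
   - *Against:* A10.1.2 describes it as approved for CHB. It is not among the test products in the synopsis or in Appendix 6-Table 2. That absence is weak evidence alone, since Appendix 10-Table 1 labels it an IMP. A10.3 names IMPs and NMEs side by side. A10.12.2 refers to the PK profiles of a single NME, where the parallel text for arms with two novel agents (A8.14.2, A11.11.1, A12.14.2) refers to two. Appendix 10-Table 2 lists PEG-IFN apart from the all-NME criteria.
   - *For:* A10.11 speaks of 'other' NME criteria after naming PEG-IFN. Section 8.3.8.2 describes study treatment in the treatment arms as the NME combination plus NUC, which leaves PEG-IFN nowhere else to sit.
   - *Result:* the documents do not settle it. The weight is towards 'not an NME'.

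2. **Declining liver function.**
   - If PEG-IFN is an NME, Table 2 and Section 8.3.8.3 discontinue it.
   - If it is not, both rules discontinue siRNA and continue NUC, and neither mentions PEG-IFN. Its own block has no row for the event. What remains is indirect: the Section 7.1 list of possible reasons for stopping study treatment (jeopardised safety, decompensation); A10.10, which modifies the dose first and stops PEG-IFN if intolerance persists; and a reference to local prescribing information.

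3. **ALT above 10×ULN, function preserved.**
   - Section 8.3.8.3: interrupt NMEs immediately.
   - Appendix 10-Table 2, PEG-IFN block: interrupt when the elevation is persistent. No duration or number of repeat values is given.
   - PEG-IFN is interrupted under both. If it is an NME, the two instructions differ on when.

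4. **Pregnancy, combination arms.** Table 2 continues NUC. Appendix 5 stops study treatment without exception. Section 6 includes marketed products in that term, Section 8.3.8.2 counts NUC in it, and Appendix 10-Table 1 lists NUC under its study-treatment heading. The two instructions for NUC are opposite.

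5. **Pregnancy, control arm.** Table 2 does not apply. Appendix 5 and the Section 7.1 list of reasons both speak of study treatment. Appendix 7-Table 1 shows NUC as the only one, so on their wording they reach it.

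6. **Scale.** A10.10.1 gives ALT elevation as a reason for PEG-IFN dose modification in 11%, and any modification in 40%. In an arm of 30 this is 0.11 × 30 = 3.3 participants if the 11% is of all participants, or 0.11 × 0.40 × 30 = 1.3 if it is of those modified. Neither counts ALT above 10×ULN or declining function, so neither measures this problem.

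**The case against.** The strongest reply is that PEG-IFN is not left without rules. Its block in Appendix 10-Table 2 reduces the dose and then interrupts as ALT rises. Section 8.3.8.3 calls for twice-weekly repeats above 10×ULN and PEG-IFN is given weekly, so a repeat value would usually be available before the next dose. A reader might infer that PEG-IFN can run on through ALT above 10×ULN with no rule to stop it. The documents do not support that, because the row quoted is the rule that interrupts it. Only the undefined 'persistent' and the mismatch with 'immediately' remain.

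On declining function, Appendix 10-Table 2 covers the whole arm and sends liver tests to Sections 7.1 and 8.3.8.3, and Section 7.1 allows study treatment to be stopped for safety. This shows the event is not ignored. It does not answer the question, because the sections referred to act on NMEs, and the Section 7.1 list gives possible reasons, not an instruction. Whether local prescribing information closes the gap cannot be judged from these documents.

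Separate triggers for siRNA and PEG-IFN may also be intended. That is a legitimate choice, and nothing here requires a shared one.

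On pregnancy, the Table 2 cell is blank in the available text, and NUC is a non-investigational background drug except in the UK. The first is a fair caution. The second does not help, since the Section 6 definition does not depend on investigational status.

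**Conclusion.** Two inconsistencies stand. First, no protocol rule clearly says what happens to PEG-IFN in arm 5 when ALT rises with declining liver function; for ALT above 10×ULN the gap is narrower and concerns timing only. Second, in the combination arms the protocol appears both to continue and to stop NUC in pregnancy. In the control arm the wording reaches the only study treatment, without saying whether that is meant.

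Three further readings go too far:
- A reader might infer that 'study treatment' is also the wrong term for the drugs given. By Section 6 it covers PEG-IFN and NUC; 'NMEs' is the unclear term.
- A reader might infer that the control arm also has two conflicting instructions. Table 2 excludes that arm.
- A reader might take the 11% and 40% as the number of participants affected. They cover ALT-driven modification at any level and modification for any reason.

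The number of affected events cannot be derived from the documents. The liver point concerns one arm of about 30. The matter is still more than missing detail, because the texts give unclear or opposite stop instructions bearing on participant safety.

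The conclusion assumes that the Table 2 action next to pregnancy is a merged cell. It places no weight on the PEG-IFN interruption row naming no drug, which may be lost text.

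**What to change.** Reconcile Section 7.1 Table 2, Section 8.3.8.3, Appendix 5 Section 4 and Appendix 10-Table 2 (with A10.11):

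- State whether PEG-IFN falls under 'NMEs'.
- In the ALT, hepatic-impairment and pregnancy rows that apply to arm 5, name siRNA, PEG-IFN and NUC individually, so that each drug has a stated action.
- Either define 'persistent' in the PEG-IFN rows or align it with Section 8.3.8.3. If different triggers are intended, say so.
- State which drugs Appendix 5 means by study treatment, including in the control arm, and make Table 2 agree for the combination arms.

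Which instruction is right in each case is for the sponsor's clinicians; this point asks only that the texts agree. The cost is amendment wording and a letter to sites, with no new procedures or participants.

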Appendix 11 Study Details Specific to siRNA (RO7445482) + CpAM (RO7049389) + NUC Arm

[figure not shown]
An overview of short interfering RNA (siRNA) + core protein allosteric modulator (CpAM) + nucleos(t)ide (NUC) treatment arm is shown in Appendix 11-Figure 1.

Participants will receive RO7445482 (also known as DCR-HBVS; 200 mg every 4 weeks [Q4W]) and RO7049389 (600 mg once a day [QD]) in addition to their background NUC therapy for the 48-week treatment period. At the end of the treatment period, participants will continue NUC treatment during the follow-up unless the NUC discontinuation criteria have been met (see Section 6.8).

Approximately 30 participants will be randomized to this treatment arm.

If a 30% delta for hepatitis B surface antigen (HBsAg) loss is observed at Week 48 (end-of-treatment [EOT]) or follow-up Weeks 12 or 24 (primary endpoint) the treatment arm may be expanded to accrue additional efficacy and safety data, and to contribute to Phase 3 design planning. If a successful interim analysis is observed at Weeks 12 or 24, shorter treatment duration arms (12 and 24 weeks' duration) and/or a response-guided therapy (RGT) arm may be added.

Appendix 11-Figure 1 siRNA + CpAM + NUC Treatment Arm

A11.1 BACKGROUND SPECIFIC TO siRNA + CpAM + NUC ARM

A11.1.1 BACKGROUND ON RO7445482

RO7445482 (DCR-HBVS) is an siRNA conjugated to N-acetyl-D-galactosamine (GalNAc), which enables liver-targeting through binding to the asialoglycoprotein receptor (ASGPR) that is highly expressed in the liver. After forming the RNA-induced silencing complex (RISC), the RO7445482 antisense strand targets hepatitis B virus (HBV) RNA for degradation by triggering RNAi-mediated cleavage within the HBsAg coding sequence, thereby inhibiting HBV gene expression.

Literature indicates that HBV antigens suppress the host immune response through several pathways, including the direct effects of long-term exposure to high concentration of viral antigens resulting in T-cell immune tolerance and T-cell exhaustion (Hai-Jun et al 2015). Depletion of viral antigens through inhibition of HBV gene expression may therefore facilitate the restoration of the host immune response.

Non-clinical studies with RO7445482 have shown potent antiviral activity. HBsAg reductions of up to 3.5 log₁₀ for more than 7 weeks, as well as significant reductions in HBcAg, were observed after a single dose in mice, demonstrating duration of action suitable for infrequent dosing.

To date, clinical experience with RO7445482 is based on a Phase I clinical study (DCR-HBVS-101) involving healthy volunteers and participants with chronic hepatitis B (CHB).

A11.1.2 BACKGROUND ON RO7049389

RO7049389 is a CpAM and belongs to the well-studied class of heteroaryldihydropyrimidine (HAP) compounds. This class of compounds induces formation of abnormal HBV core protein aggregates, which are subsequently recognized and depleted. Depleting functional core protein results in interruption of viral assembly and inhibition of HBV replication.

The HBV core protein is involved in multiple steps of the viral life cycle such as encapsulation of pre-genomic ribonucleic acid (pgRNA), subsequent initiation of reverse transcription, and is an important component of covalently closed circular DNA (cccDNA) mini-chromosome. Furthermore, literature suggests that the HBV core protein may play a role in suppressing host innate immune responses (Twu et al 1988; Fernandez et al 2003; Gruffaz et al 2013). Depletion of functional core protein may therefore facilitate host immune restoration. RO7049389 can therefore potentially provide anti-HBV benefits by both direct inhibition of viral replication and augmentation of host immune responses against the virus.

RO7049389 has shown potent antiviral activity through the induction of HBV core protein misassembly and subsequent degradation, and has a high degree of selectivity against HBV. RO7049389 demonstrated activity against most prevalent HBV genotypes (A, B, C, D) and against a panel of NUC analogue-resistant HBV variants tested in vitro.

To date, clinical experience with RO7049389 includes three Phase 1 clinical studies: an entry-into-human (EIH) study in healthy volunteers (HV) and patients (YP39364), a study in HVs of Chinese descent (YP39406), and a drug-drug interaction (DDI) study in HVs (YP40218).

A11.2 BENEFIT/RISK ASSESSMENT SPECIFIC TO siRNA+ CpAM + NUC ARM

The 48-week treatment with RO7445482 and RO7049389 in combination with NUC aims to result in therapeutic benefit for participants, including possibly higher functional cure rates than observed currently with standard-of-care therapies (monotherapy with NUC or PEG-IFN). The concurrent RO7445482 and RO7049389 administrations aim is to test the hypothesis whether prolonged reduction in HBV antigens, including but not limited to HBsAg, will result in immune-restoration and potentially functional cure.

In non-clinical rodent pharmacology studies, RO7445482 (DCR-HBVS) treatment resulted in a lowering of serum HBsAg of up to $3.5 \log_{10}$ for > 7 weeks after a single, translationally relevant dose. Serum HBsAg levels did not return to within $2 \log_{10}$ of baseline for at least 4 months, demonstrating duration of action suitable for infrequent dosing. These data support the use of DCR-HBVS in patients with CHB, who will require a sustained host response to achieve a functional cure.

Emerging clinical trial data shows that CpAM exerts additional anti-viral activity when combined with NUC (Man-Fung Yuen et al 2020). This was demonstrated by the greater decline in HBV DNA and pgRNA levels, as well as the proportion of patients achieving undetectable HBV DNA and pgRNA levels.

Interim Phase 1 data have shown significant and durable antiviral activity with 4 monthly doses of RO7445482 in NUC-suppressed participants with CHB. At Day 112, mean HBsAg \log_{10} IU/mL reduction from baseline were 1.39, 1.80, and 1.84 for participants who received 1.5 mg/kg, 3.0 mg/kg or 6 mg/kg, respectively. Approximately 80% of participants achieved > 1.5 \log_{10} IU/mL reduction (irrespective of HBeAg-status), 60% had HBsAg levels < 100 IU/mL, and durability of response was demonstrated up to Day 392.

Based on the interim Phase 1 data, RO7445482 was safe and well tolerated in healthy volunteers (HV) and CHB patients. The safety profile appears to be similar between HVs and patient participants, and there were no safety signals or dose related trends identified. No severe or serious treatment-emergent adverse events (TEAEs) or TEAEs leading to treatment discontinuation, apart from generally mild injection site reactions (ISRs), there was absence of other potential oligonucleotide class effects.

RO7445482 and RO7049389 have shown acceptable safety/tolerability in the Phase 1 studies involving healthy volunteers and CHB participants, and non-clinical toxicology and safety pharmacology studies support the proposed 48-week combination regimen.

For details, refer to the RO7445482 and RO7049389 Investigator's Brochures.

A11.3 JUSTIFICATION FOR DOSE SPECIFIC TO siRNA+ CpAM + NUC ARM

For RO7445482, fixed dose of 200 mg Q4W (equivalent to 3 mg/kg monthly) has been selected for Phase 2 study in combination with other IMPs/NMEs. This dose is within the anticipated therapeutic dose-range in humans and is expected to be safe and well tolerated. A summary of the key data supporting the selected dose is provided below:

- The dose-response trend in the HBsAg declines, together with PK/PD modeling of interim Phase 1 data, supports the proposed 200 mg Q4W dosing regimen. Preliminary PK/PD modeling predicts that the proportion of participants who will achieve > 1.5 and > 2 log₁₀ IU/mL reductions in HBsAg, following Q4W doses up to Week 12, will be higher with a 200 mg Q4W regimen (97% and 56%, respectively) compared to a 100 mg Q4W regimen (89% and 6%, respectively).
- The non-clinical chronic toxicology studies provide acceptable safety margins for the 200 mg Q4W fixed dose (3 mg/kg equivalent) for treatment period of 48 weeks.
- PK/PD modelling supports use of fixed (200 mg) instead of weight based (3 mg/kg) RO7445482 dosing

For RO7049389, a dose of 600 mg QD has been selected for this Phase 2 study. This dose is within the predicted therapeutic dose-range in humans and is expected to be safe and well tolerated. A summary of the key data supporting the selected dose is provided below:

- RO7049389 doses up to 1000 mg QD (for 28 days), 800 mg BID (for 6 days) and 2500 mg (single dose) have been observed to be safe and well tolerated in three Phase 1 studies involving healthy volunteers and CHB participants.
- Although 200 mg to 600 mg QD doses resulted in robust pharmacodynamic effects (HBV DNA decline 2.66 – 3.2 log₁₀ IU/mL) in the Phase 1 studies, a trend of increased HBV DNA decline was observed with higher doses. In addition, diseasemodelling utilizing non-clinical and clinical PK/PD data predicts an increased PD effect with the 600 mg QD dose.
- The non-clinical chronic toxicology studies provide acceptable safety margins for the 600 mg QD dose.

Further details are provided in the RO7445482 and RO7049389 Investigator's Brochures.

A11.4 INCLUSION/EXCLUSION CRITERIA SPECIFIC TO SIRNA + CpAM + NUC ARM

Participants must meet the following criterion for inclusion in the siRNA + CPAM + NUC treatment arm:

Sex

1. Female Participants:

A female participant is eligible to participate if she is not pregnant, not breastfeeding, and at least one of the following conditions applies:

- Woman of non-childbearing potential (WONCBP).
- Woman of childbearing potential (WOCBP), who:
 - Agrees to remain abstinent (refrain from heterosexual intercourse) or use 2 acceptable contraceptive methods, of which at least one is considered highly effective (result in a failure rate of < 1% per year during the treatment period and for at least 6 months after the final dose of study treatment (ref A11.6 and Appendix 5).
 - Has a negative pregnancy test at screening (Day -14 to -7). In addition, willing to undergo a urine pregnancy test at Day 1 and every month during treatment and up to 6 months follow-up, thereafter every 3 months until end of follow-up.

A11.5 LIFESTYLE CONSIDERATIONS SPECIFIC TO siRNA + CpAM + NUC ARM

RO7049389 will be given in fasted state (at least 2 hours after a meal or 2 hours before the next meal). NUCs will be given according to the local prescribing information.

For RO7049389, any nutrients known to modulate activity of CYP enzymes (e.g., grapefruit- or Seville orange-containing products) will be prohibited within 3 days before Day -1 through to the last dose of RO7049389.

For CHB participants who routinely take herbal medicines that in Investigator's opinion may have immune-modulatory effects, herbal medicines should strongly be discouraged.

A11.6 CONTRACEPTIVE REQUIREMENTS SPECIFIC TO SIRNA + CpAM + NUC ARM

For WOCBP: agreement to remain abstinent (refrain from heterosexual intercourse) or use 2 acceptable contraceptive methods of which at least 1 is considered highly effective (see Appendix 5), during the study and for at least 6 months after the last dose of study drug.

- Examples of acceptable highly effective contraceptive methods (< 1% failure rate per year) include combined or progesterone-only hormonal contraception, intrauterine device, and vasectomized partner.
- Examples of acceptable not as highly effective contraceptive methods (> 1% failure rate per year) include progesterone only hormonal contraception (where inhibition of ovulation is not the primary mode of action) and male or female condoms with or without spermicide.

For men: agreement to remain abstinent (refrain from heterosexual intercourse) or agree to use contraceptive measures, and agree to refrain from donating sperm, as defined below:

- Men must remain abstinent or use a condom during the treatment period and for at least 6 months after the last dose of study drug to avoid exposing the embryo.
- Men must refrain from donating sperm during this same period.

The reliability of sexual abstinence should be evaluated in relation to the duration of the clinical trial and the preferred and usual lifestyle of the participant. Periodic abstinence (e.g., calendar, ovulation, symptothermal, or post-ovulation methods) and withdrawal are not acceptable methods of contraception.

A11.7 TREATMENT ADMINISTERED SPECIFIC TO siRNA + CpAM + NUC ARM

